### **Sensitivity Analysis for primary endpoint**

Mixed models repeated measures (MMRM) analysis based on both imputed data and observed data will be used as sensitivity analysis. The explanatory variables will include treatment, week, baseline value, baseline lipid lowering medications, treatment-by-week interaction, and treatment-by-baseline interaction, with unstructured covariance model across week. The average treatment effect at Week 16 (lsmeans with 95% CI for each treatment group and lsmean difference with 95% CI) will be provided as both tables and figures. Additional MMRM analyses may include the addition of other model covariates such as age at baseline, sex, and baseline FIB-4 (dichotomized at  $\geq 1.3$ ). An additional series of models may include percent change from baseline as the dependent variable.

A plot of fitted values versus residuals and the residual QQ Plot will be used to check the ANCOVA model assumptions. If there are concerns about the model assumptions, i.e., normality and homogeneity of variances, a non-parametric ANCOVA based on the rank scores will be used as a sensitivity analysis as well.

### **Secondary Efficacy Endpoints**

A summary of descriptive statistics of the absolute change from baseline to week 16 in liver fat fraction (%) as measured by MRI-PDFF and total liver fat (mL) as measured by MRI will be provided.

The test results and changes from baseline at each scheduled time point, including week 16 and Follow-up, will be summarized for the following variables:

- Serum ALT, AST, and gamma-glutamyl transferase
- HDL-C, non-HDL-C, LDL-C/HDL-C ratio, and triglycerides
- Total bile acids

The minimum and maximum post baseline value for each above lab test will be included in the visit summaries.

The change from baseline at week 16 will be analyzed using the analysis of covariance (ANCOVA) with the treatment group as a factor and the corresponding baseline value as a covariate. The model assumptions for each secondary efficacy endpoint will be evaluated before the analysis. If there are concerns about the model assumptions, i.e., normality and homogeneity of variances, non-

parametric ANCOVA based on the rank scores will be used. No missing data imputation for secondary efficacy endpoints.

MMRM figures of change from baseline by study arm and the difference between study arms will be generated for all secondary endpoints.

## Exploratory Efficacy Endpoints

The test results and change from baseline (unless otherwise specified) to week 4, week 8, week 12, week 16, and follow-up, will be summarized for the following variables:

- Fasting glucose, insulin, homeostatic model assessment-insulin resistance, HbA1c, free fatty acids
- GLP-1, FGF-19, and C4 levels
- High-sensitivity CRP
- Lanosterol and beta-sitosterol
- Body weight, BMI, waist circumference, and waist-to-hip ratio (Physical examination)
- Apolipoprotein A1 and Apolipoprotein B
- Fibrosis and inflammation markers: FIB-4, APRI and NFS

By patient figures (spaghetti plots) plots for the absolute value and change from baseline over time will be provided for each efficacy endpoint. An MMRM of change from baseline will be provided for all efficacy endpoints. Two plots for each MMRM analysis will be provided, one figure by treatment arm, and a second figure for the contrast between treatment arms. Correlation matrices will be provided for efficacy endpoints overall, by treatment, and by treatment by study visit.

$$\text{FIB-4} = [\text{Age (years)} \times \text{AST (U/l)}] / [\text{Platelet}(\times 10^9/l) \times (\text{ALT(U/l)})^{0.5}]$$

$$\text{APRI} = [\text{AST (IU/l)} / \text{AST (ULN)}] / \text{Platelet}(\times 10^9/l) \times 100$$

$$\begin{aligned} \text{NAFLD fibrosis score} = & -1.675 + 0.037 \times \text{age (years)} + 0.094 \times \text{BMI (kg/m}^2\text{)} + 1.13 \times \\ & \text{IFG/diabetes (yes} = 1, \text{no} = 0\text{)} + 0.99 \times \text{AST/ALT ratio} - 0.013 \times \text{platelet}(\times 10^9/l) - 0.66 \times \\ & \text{albumin (g/dl)} \end{aligned}$$

Additional analyses may be performed to identify differences in treatment effect by baseline characteristics, such as dichotomized subjects by FIB-4 <1.3, and  $\geq 1.3$ , BMI ( $<30/\geq 30$ ), type 2 diabetes (Y/N), cardiovascular co-morbidities (Y/N), lipid lowering concomitant medications (Y/N), and LDL-C (by  $</\geq$  median value).

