### **7.2.2      Exclusion Criteria**

Patients who meet any of the following criteria will not be included in the study:

1. Women who are pregnant, breastfeeding, or plan to become pregnant during the study
2. Body mass index (BMI)  $<25 \text{ kg/m}^2$
3. Fibrosis-4 index (Fib-4)  $>2.6$
4. Any of the following laboratory abnormalities:
  - a. ALT  $>5 \times$  upper limit of normal (ULN) or AST  $>5 \times$  ULN
  - b. International normalized ratio (INR)  $\geq 1.3$ , unless on anticoagulant therapy
  - c. Total bilirubin  $>$ ULN, except with an established diagnosis of Gilbert's syndrome
  - d. Platelet count less than the lower limit of normal (LLN)
  - e. Creatinine clearance as calculated by the modification of diet in renal disease (MDRD) estimated glomerular filtration rate (eGFR) equation  $<60 \text{ mL/min}$

NOTE: Unless otherwise specified, repeat testing may be performed in consultation with the Medical Monitor.

5. Acute or chronic liver disease other than NAFLD/NASH including but not limited to the following:
  - a. Hepatitis B (as defined by the presence of hepatitis B surface antigen at screening) or hepatitis C (as defined by the presence of hepatitis C virus [HCV] antibody [anti-HCV]). Patients with positive anti-HCV who test

negative for HCV ribonucleic acid at screening will be allowed to participate in the study as long as there is evidence of viral negativity for a minimum of 12 months prior to screening)

- b. Evidence of autoimmune hepatitis
- c. History of primary biliary cholangitis, primary sclerosing cholangitis, Wilson's disease, homozygous alpha-1-anti-trypsin deficiency, hemochromatosis or iron overload, drug-induced or alcoholic liver disease, or known bile duct obstruction
- d. Suspected or proven hepatocellular carcinoma
6. Known history of human immunodeficiency virus
7. Medical history of liver cirrhosis
8. Clinical evidence of portal hypertension to include any history of ascites, hepatic encephalopathy, or presence of esophageal varices
9. Use of drugs historically associated with NAFLD (amiodarone, methotrexate, systemic glucocorticoids, tetracyclines, tamoxifen, estrogens at doses greater than those used for hormone replacement, anabolic steroids, or valproic acid) or other known hepatotoxins for >2 weeks in the year prior to screening
10. Use of the following medications:
  - a. GLP-1 agonists unless on a stable dose 3 months prior to liver biopsy or Screening

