  - b. Ursodeoxycholic acid, thiazolidinediones, or obeticholic acid within 3 months prior to Screening
  - c. Statins and other lipid-modifying therapies must have been stable for  $\geq 3$  months prior to Screening
  - d. Oral antidiabetic drugs (other than those specifically excluded) must have been stable for  $\geq 3$  months prior to Screening

- e. Agents (including herbal over-the-counter weight-loss preparations) or medications known to significantly impact body weight within 3 months prior to Screening (e.g., sibutramine, phenetamine, and orlistat)
- 11. History of significant alcohol consumption, defined as an average of >20 g/day in female patients and >30 g/day in male patients, for a period of >3 consecutive months within 1 year prior to Screening, hazardous alcohol use (Alcohol Use Disorders Identification Test score ≥8), or an inability to reliably quantify alcohol consumption based upon judgment of the Investigator
- 12. Weight change ≥10% within the 6 months prior to Screening or ≥5% within the 3 months prior to Screening
- 13. Prior or planned (during the study period) bariatric surgery (e.g., gastroplasty, sleeve gastrectomy and roux-en-Y gastric bypass)
- 14. Type 1 diabetes by medical history
- 15. Uncontrolled Type 2 diabetes defined as hemoglobin A1c (HbA1c) >9.5% at Screening (patients with HbA1c >9.5% may be rescreened) or requiring oral diabetes medication dose adjustment >10% within 2 months prior to Screening
- 16. Clinical hyperthyroidism or hypothyroidism or screening hormone results pointing to thyroid dysfunction. Patients receiving dose-stable thyroid replacement therapy for ≥3 months prior to Screening will be allowed to participate as long as thyroid tests (thyroid-stimulating hormone/triiodothyronine/thyroxine) show that the patient is euthyroid
- 17. History of any condition causing malabsorption such as chronic pancreatitis, extensive bowel/small intestine surgery, celiac disease, or bile flow obstruction
- 18. History of any condition associated with acute or chronic diarrhea such as inflammatory bowel disease (IBD), functional diarrhea, irritable bowel syndrome (IBS) with predominant diarrhea, IBS with mixed bowel habits, or unclassified IBS
- 19. History of ischemic colitis

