  - b. Ursodeoxycholic acid, thiazolidinediones, or obeticholic acid within 3 months prior to Screening

- c. Statins and other lipid-modifying therapies must have been stable for  $\geq 3$  months prior to Screening
- d. Oral antidiabetic drugs (other than those specifically excluded) must have been stable for  $\geq 3$  months prior to Screening
- e. Agents (including herbal over-the-counter weight-loss preparations) or medications known to significantly impact body weight within 3 months prior to Screening (e.g., sibutramine, phenetamine, and orlistat)

11. History of significant alcohol consumption, defined as an average of  $>20$  g/day in female patients and  $>30$  g/day in male patients, for a period of  $>3$  consecutive months within 1 year prior to Screening, hazardous alcohol use (Alcohol Use Disorders Identification Test score  $\geq 8$ ), or an inability to reliably quantify alcohol consumption based upon judgment of the Investigator

12. Weight change  $\geq 10\%$  within the 6 months prior to Screening or  $\geq 5\%$  within the 3 months prior to Screening

13. Prior or planned (during the study period) bariatric surgery (e.g., gastroplasty and roux-en-Y gastric bypass)

14. Type 1 diabetes by medical history

15. Uncontrolled Type 2 diabetes defined as hemoglobin A1c (HbA1c)  $>9.5\%$  at Screening (patients with HbA1c  $>9.5\%$  may be rescreened) or requiring insulin dose adjustment  $>10\%$  within 2 months prior to Screening

16. Clinical hyperthyroidism or hypothyroidism or screening hormone results pointing to thyroid dysfunction. Patients receiving dose-stable thyroid replacement therapy for  $\geq 3$  months prior to Screening will be allowed to participate as long as thyroid tests (thyroid-stimulating hormone/triiodothyronine/thyroxine) show that the patient is euthyroid

17. History of any condition causing malabsorption such as chronic pancreatitis, extensive bowel/small intestine surgery, celiac disease, or bile flow obstruction

18. History of any condition associated with acute or chronic diarrhea such as inflammatory bowel disease (IBD), functional diarrhea, irritable bowel syndrome

(IBS) with predominant diarrhea, IBS with mixed bowel habits, or unclassified IBS

19. History of ischemic colitis

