## 1 INTRODUCTION

The purpose of this statistical analysis plan (SAP) is to describe the procedures and the statistical methods that will be used to analyze and report efficacy and safety data for study A3309-012 based on protocol dated on 10 September 2019 (version 3.0).

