## 2.2 DEFINITIONS OF ANALYSIS SETS

### ITT Population

The intent-to-treat (ITT) population will include all patients who are randomized in the study and receive at least 1 dose of study drug. The ITT population will be used for all efficacy analyses based on the treatment randomized unless otherwise specified.

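### Insulin and HOMA-IR are analysed in all ITT patients, although Version 3.0 does not exclude insulin-treated type 2 diabetics, in whom HOMA-IR cannot be interpreted

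*SAP*

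**What the plan says.** The SAP introduction states that it is "based on protocol dated on 10 September 2019 (version 3.0"), so the Version 3.0 eligibility criteria govern.

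**Who can enter.** In Protocol Version 3.0, section 7.2.2, exclusion 14 is "Type 1 diabetes by medical history". Exclusion 15 covers HbA1c above 9.5% or "requiring oral diabetes medication dose adjustment >10% within 2 months prior to Screening". Exclusion 10d requires stability of oral antidiabetic drugs only. Exclusion 10a bars "GLP-1 agonists unless on a stable dose 3 months prior to liver biopsy or Screening". No criterion names insulin. In section 7.2.1, inclusion 3b counts drug treatment for raised glucose towards the metabolic-syndrome diagnosis and makes no exception for insulin. Section 8.7 has medication changes recorded and prohibits no drug.

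**What is analysed.** SAP 3.2 lists "Fasting glucose, insulin, homeostatic model assessment-insulin resistance, HbA1c, free fatty acids" as exploratory endpoints, to be summarised by visit, and adds: "An MMRM of change from baseline will be provided for all efficacy endpoints". SAP 2.2 sets the population: "The ITT population will be used for all efficacy analyses based on the treatment randomized unless otherwise specified". For insulin use there is no restriction, flag, covariate or sensitivity analysis.

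**The concern.** HOMA-IR is built from fasting glucose and fasting insulin, and it reads the insulin value as what the patient's own pancreas is secreting. In a patient who injects insulin, that reading fails. If the assay detects the injected product, the value depends on dose and time since injection. If it does not, the value reflects the patient's own secretion as altered by the injected insulin. Either way a dose change between visits can look like a change in insulin resistance.

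Protocol section 5.3 names improved insulin sensitivity through GLP-1 as one of the mechanisms by which the drug might help, and insulin and HOMA-IR are its direct readouts. With 23 patients planned per arm, one odd value carries weight. A rank-based fallback is written for the primary and secondary endpoints in SAP 3.2 but not for the exploratory ones, so an extreme value keeps its full leverage in the MMRM.

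**Working it through.** The plan gives no effect size, SD or power to reproduce: SAP 1.3 says that 46 patients (23 per arm) were chosen on clinical experience. Two questions can be checked: whether such patients can be in the analysis, and how much one of them could matter.

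**Step 1: eligibility.** Each rule that bears on glucose-lowering treatment in Version 3.0 covers something other than insulin: type 1 diabetes (exclusion 14), HbA1c and oral dose changes (15), oral-drug stability (10d), and GLP-1 agonist stability (10a). An insulin-treated type 2 diabetic with HbA1c of 9.5% or below can satisfy all of them. Version 2.0 had, in exclusion 15, "or requiring insulin dose adjustment" of more than 10%. Version 3.0 refers to oral medication instead. The change is not itself an error, but it shows that insulin users had been considered, and no insulin-stability rule remains.

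**Step 2: shift in the arm mean.** Inputs: n = 23 per arm (SAP 1.3). Assumptions not in the documents: HOMA-IR = glucose (mg/dL) x insulin (uU/mL) / 405; glucose 150 mg/dL; d = change in one patient's measured insulin that is due to injected insulin, 10 to 100 uU/mL.

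- Shift in mean insulin = d / 23
- Shift in mean HOMA-IR = (150 x d / 405) / 23

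| d (uU/mL) | Mean insulin shift | Mean HOMA-IR shift |
|---|---|---|
| 10 | 0.43 | 0.16 |
| 30 | 1.30 | 0.48 |
| 50 | 2.17 | 0.81 |
| 100 | 4.35 | 1.61 |

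For d = 50: 150 x 50 / 405 = 18.52, and 18.52 / 23 = 0.81. Between glucose 120 and 180 mg/dL, the d = 50 figure runs from 0.64 to 0.97.

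**Step 3: compared with sampling error, on the insulin scale.** The SD of change is not given; assume 5, 10 or 15 uU/mL.

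- SE of an arm mean = SD / sqrt(23) = 1.04, 2.09, 3.13
- 95% half-width of the difference = 1.96 x SD x sqrt(2/23) = 2.89, 5.78, 8.67

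One patient at d = 50 moves the mean by 2.17, about 1 SE if the SD is 10 and about 2 SE if it is 5. At d = 10 the shift (0.43) is under half an SE even at SD 5.

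**Step 4: loss of precision.** The same patient inflates the arm SD to about sqrt(SD^2 + d^2/23). At d = 50, d^2/23 = 108.7.

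- SD 10: sqrt(100 + 108.7) = 14.4. The half-width becomes 1.96 x sqrt((208.7 + 100) / 23) = 7.18, against 5.78.
- SD 5: sqrt(25 + 108.7) = 11.6. The half-width becomes 1.96 x sqrt((133.7 + 25) / 23) = 5.15, against 2.89.

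**Step 5: could a few patients alone give p < 0.05?** Take k patients in one arm, all changing by the same d, and no other change in either arm. The arm mean is k x d / 23 and the arm variance is d^2 x k(23 - k) / (23 x 22), so t = sqrt(22k / (23 - k)), whatever d is.

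- k = 1: sqrt(22/22) = 1.00
- k = 2: sqrt(44/21) = 1.45
- k = 3: sqrt(66/20) = 1.82

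The two-sided 5% critical value on 44 degrees of freedom is about 2.02. Up to three patients, all moving the same way in the same arm, do not reach it unaided.

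**The case against.** The strongest reply is that the problem may not exist. Insulin users are eligible only because nothing excludes them; no section says that any were enrolled. Exclusion 27 also lets the investigator keep out a patient whose condition would interfere with the outcomes. This stands as a limit on size. It does not supply an analysis rule if such patients are present.

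Second, a reader might infer that the insulin assay is known to pick up injected insulin, and that the endpoints are therefore invalid. The documents do not support this: Protocol Table 2 and the SAP appendix name no assay, and processing instructions are left to a study reference manual. The supportable claim is narrower: HOMA-IR is not interpretable in a patient injecting insulin, whichever way the assay behaves.

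Third, a reader might infer that a few insulin users could manufacture a treatment effect. The calculation above speaks against that for one to three patients, and in a randomised, blinded trial background dose changes are mainly noise. Such patients could still shift an estimate, widen its interval or help to hide a modest effect.

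Fourth, the endpoint is change from baseline, so a constant contribution from a steady dose largely cancels. That holds for insulin itself if the dose is steady, which no rule requires. It holds less well for HOMA-IR, where the insulin value multiplies any change in glucose.

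Fifth, there are partial safeguards: medians and ranges, per-patient plots, medication listings and an optional analysis by type 2 diabetes. They would help to reveal an odd patient, but none separates insulin users or changes the modelled estimate.

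**Conclusion.** The point holds as a modest, inexpensive improvement. On the text, insulin-treated type 2 diabetics can enter under Version 3.0 with no insulin-stability rule, and SAP 3.2 would analyse their insulin and HOMA-IR values with everyone else's. If any are enrolled, each could shift a 23-patient arm mean of HOMA-IR by 0.16 to 1.61 units for a change in measured insulin of 10 to 100 uU/mL. That range rests on the assumed formula and a glucose of 150 mg/dL; if none are enrolled the effect is nil. The likelier harm is lost precision.

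A reader might extend the point to the GLP-1 endpoint because exclusion 10a allows stable GLP-1 agonists. That follows only if the assay detects those drugs, which the documents do not say. The endpoints concerned are exploratory, the study was not formally powered, and the LDL-C conclusion is unaffected.

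**What to change.** In SAP 3.2, Exploratory Efficacy Endpoints, add one paragraph:

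- Make patients not using insulin at baseline the main analysis set for insulin and HOMA-IR. Insulin use at randomisation is a pre-randomisation characteristic, so the comparison stays randomised. Report the number left out in each arm.
- Give the all-patient ITT result for both endpoints as a sensitivity analysis.
- Flag patients who start insulin after baseline and address them in a sensitivity analysis. Do not set their later values to missing in the main model: a start may follow worsening glycaemia, and the MMRM would then lean on a missing-at-random assumption and change the quantity estimated.
- Handle GLP-1 the same way for baseline GLP-1 agonist users only if the assay used detects the permitted agonists.
- Keep HbA1c and glucose in all patients as planned.

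The data are already collected: Protocol 8.7 has medications and dose changes entered in the eCRF, and SAP 3.1 codes them by ATC class. This is an analysis change only and sets no rule on eligibility or treatment. The cost is a somewhat smaller main analysis set for two exploratory endpoints: 1 to 3 insulin users in an arm would leave 22 to 20 patients there, and none would leave all 23.

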### 5.2 Background

#### 5.2.1 Nonalcoholic Fatty Liver Disease (NAFLD) and Nonalcoholic Steatohepatitis (NASH)

Recent data suggest that bile acids may play an important role in NASH pathogenesis (Ferslew 2015; Aranha 2008; Puri 2018). Bile acids are signaling molecules involved in lipid, glucose, and energy homeostasis, which are metabolic pathways linked to NAFLD/NASH and comorbidities such as metabolic syndrome, obesity, and diabetes. Bile acids as well as free cholesterol, which is the precursor from which bile acids are synthesized, can act as lipotoxic agents that drive inflammation and fibrosis. Studies have shown that both serum and liver bile acids are increased in patients with NASH, and recent data have suggested that the presence and severity of NASH is associated with specific changes in circulating bile acids (Puri 2018). Thus, targeting of bile acid pathways has therapeutic potential in patients with NASH.

The enterohepatic circulation of bile acids plays a crucial role in whole body sterol balance. Bile acids are secreted to the intestine via the bile duct and then reabsorbed, mainly by a specific bile acid transporter located in the ileum (IBAT or ASBT) and delivered back to the liver, completing the enterohepatic circulation (Prawitt 2011).

Bile acid reabsorption from the intestine is a very efficient process where 95% of the secreted bile acids are reabsorbed and IBAT appears to be the major regulator of the bile acid pool in animals and humans. IBAT inhibitors reduce the reabsorption of bile acids from the ileum and prevent their return to the liver. The liver compensates for the decrease in bile acid levels by upregulating cholesterol 7 $\alpha$ -hydroxylase, the rate-limiting

enzyme for bile acid synthesis. This results in lower hepatic cholesterol levels and an increased number of low-density lipoprotein (LDL) receptors in the liver leading to reduced plasma low-density lipoprotein cholesterol (LDL-C; [Bertolotti 2003; Naoumova 1999]). Bile acids also positively regulate glucagon-like peptide-1 (GLP-1) levels via activation of TGR5 (Prawitt 2011; Schaap 2014). GLP-1 is an insulinotropic hormone but has many other roles, e.g., slowing gastric emptying and increasing satiety signals leading to weight loss (Andersen 2018).

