
 
• Apolipoprotein A1
 
• Apolipoprotein B
 
• Chylomicron cholesterol
 
• Chylomicron triglycerides
 
• High-density lipoprotein (HDL) cholesterol
 
• Lipoprotein(a) cholesterol
 
• Low-density lipoprotein (LDL) cholesterol
 
• LDL triglyceride
 
• Non-high-density lipoprotein cholesterol
 
• Total cholesterol
 
• Triglycerides
 
• Very low-density lipoprotein (VLDL) cholesterol
 
• VLDL triglyceride
 
• Lanosterol
 
• Beta-sitosterol
 
	
 
• High-sensitivity C-reactive protein (CRP)
 
• C4
 
• Fibroblast growth factor-19 (FGF-19)
 
• Fibrosis and inflammation markers: FIB-4, APRI, and NAS
 
• Glucagon-like peptide-1 (GLP-1)
 
	
 
• Follicle-stimulating hormone
 
• Homeostatic model assessment-insulin resistance
 
• Insulin
 
• Thyroxine
 
• Triiodothyronine
 
• Thyroid-stimulating hormone
 
• Free fatty acids
 
• Adipose tissue insulin resistance
 
• Adiponectin
 

BILE ACIDS (FASTING)	PREGNANCY	SEROLOGY

 
• Total bile acids
 
	
 
• Serum
 
• Urine
 
	
 
• Hepatitis B virus surface antigen
 
• Hepatitis C virus antibody and ribonucleic acid
 

 LDL-cholesterol will be determined by calculation when triglyceride levels are less than or equal to 400 mg/dL, LDL-C will be determined by preparative ultracentrifugation (PUC) when triglyceride levels are greater than 400 mg/dL.

 A postmenopausal state is defined as no menses for ≥12 months without an alternative medical cause. A follicle-stimulating hormone level in the postmenopausal range will be used to confirm a postmenopausal state in women ≤55 years of age, performed at Screening visit only.

 Thyroid function test will be performed during Screening visit only.

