## SAS sample code for MMRM

```
proc mixed data=mmrm method=reml;
  class trtp usubjid week lipid_low;
  model chg= trtp base lipid_low trtp*base week trtp*week;
  repeated week/ type = un subject=subnum;
  lsmeans week /pdiff cl;
  ods output lsmeans = lsmeans ;
run;
```

*Note: variables included in the model and class statement varies for different endpoints;*

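### Lanosterol and beta-sitosterol are analysed only as uncorrected concentrations, so an arm difference cannot be separated from the cholesterol fall the drug is meant to cause

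*SAP*

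**What the plan says.** Protocol 9.1.3 and SAP 1.2 and 3.2 name "Lanosterol and beta-sitosterol" among the exploratory efficacy endpoints, with no denominator. For this group of variables the SAP states: "The test results and change from baseline (unless otherwise specified) to week 4, week 8, week 12, week 16, and follow-up, will be summarized". It adds "An MMRM of change from baseline will be provided for all efficacy endpoints", and by-patient "plots for the absolute value and change from baseline over time will be provided for each efficacy endpoint".

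Two further provisions could bear on the point. One is "Correlation matrices will be provided for efficacy endpoints overall, by treatment, and by treatment by study visit". The other is a note to the MMRM sample code that "variables included in the model and class statement varies for different endpoints"; no variable is named there for the sterols.

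The protocol's background (5.2.1) gives the intended mechanism: lower hepatic cholesterol and an "increased number of low-density lipoprotein (LDL) receptors in the liver leading to reduced plasma low-density lipoprotein cholesterol". Change in LDL-C at Week 16 is the primary endpoint.

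"Total cholesterol" stands in the same fasting lipid profile as both sterols (protocol Table 2; SAP Appendix, Laboratory Parameters). That profile is scheduled at all seven visits. The SAP Appendix marks both sterols as exploratory efficacy endpoints and leaves total cholesterol unmarked. Total cholesterol is therefore reported through the laboratory summaries of SAP 3.4.

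**The concern.** The arms are expected to diverge in plasma cholesterol after baseline, because that is what the trial tests. If a sterol is carried with cholesterol, removing the carrier lowers the sterol's concentration even when the amount per unit of cholesterol has not changed. Baseline adjustment cannot remove this, since the divergence arises after randomisation.

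The two sterols are commonly read as indicators of cholesterol synthesis (lanosterol) and absorption (beta-sitosterol). Neither document states this, but it is the usual reason to measure them. Read that way, a fall in beta-sitosterol could be carrier loss rather than reduced absorption. A compensatory rise in synthesis could be blunted, or even reversed in sign, in the lanosterol concentration. What is at stake is the interpretation of two exploratory markers.

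**Working it through.** There is no figure in the plan to reproduce. The sample size has no power calculation, and no effect size or SD is given for LDL-C, total cholesterol or either sterol.

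**Inputs from the documents**
- 23 patients per arm (SAP 1.3).
- Two-sided 5% level (SAP 2.1).
- Sterols and total cholesterol in one fasting panel at each visit.

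**Inputs assumed**
- f, the fall in total cholesterol relative to placebo: 5-20%.
- r, the relative change in the sterol/cholesterol ratio: -10% to +50%.
- SD of the log change: 0.2-0.4.
- The sterol tracks total cholesterol proportionally.

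**Step 1: the identity.** Concentration = ratio x total cholesterol, so

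change in concentration = (1 + r)(1 - f) - 1.

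| True ratio change r | f = 5% | f = 10% | f = 15% | f = 20% |
|---|---|---|---|---|
| -10% | -14.5% | -19.0% | -23.5% | -28.0% |
| 0 | -5.0% | -10.0% | -15.0% | -20.0% |
| +10% | +4.5% | -1.0% | -6.5% | -12.0% |
| +20% | +14.0% | +8.0% | +2.0% | -4.0% |
| +50% | +42.5% | +35.0% | +27.5% | +20.0% |

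The ratio rise that leaves the concentration flat is 1/(1 - f) - 1, which is 5.3%, 11.1%, 17.6% and 25.0% for the four falls.

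**Step 2: how often the carrier effect alone reaches nominal significance.** With r = 0 the log effect is ln(1 - f). The chance of p < 0.05 in the direction of the effect is approximately

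Φ( |ln(1 - f)| / (SD x √(2/23)) - 1.96 ).

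For f = 10% and SD = 0.3: 0.1054 / (0.3 x 0.2949) = 1.19, and Φ(1.19 - 1.96) = 22%.

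| SD of log change | f = 5% | f = 10% | f = 15% | f = 20% |
|---|---|---|---|---|
| 0.2 | 14% | 43% | 79% | 97% |
| 0.3 | 8% | 22% | 45% | 71% |
| 0.4 | 6% | 14% | 28% | 47% |

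**Step 3: what a real marker change loses.** Take r = +20% and SD 0.3 for both forms. Power is 54% on the ratio. On the concentration it is 14% at f = 10% and 4% at f = 15%. The last figure is below 5% because only the correct direction is counted.

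**Step 4: whether a planned analysis already removes the effect.**
- Percent change, which protocol 11.2.2.1 allows, does not. The identity above is already in relative terms.
- The correlation matrices are descriptive and cover efficacy endpoints, of which total cholesterol is not one. They give no corrected treatment contrast.
- The note that model variables vary by endpoint leaves room for a cholesterol term but does not specify one.
- The laboratory summary of total cholesterol gives its mean change by arm, separately from the sterols. That does not yield a within-patient ratio or its standard error.

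**The case against.** The strongest objection is that the premise lies outside the documents. They name the two analytes but do not say that lipoproteins carry them or what they mark, and protocol 5.2.1 speaks only of LDL-C. That is correct, and the premise must be stated as an assumption. It is general lipid physiology rather than a figure taken from one source, and the sterols' place in the lipid profile is consistent with it.

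Other objections stand in part:

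- **Size.** Every fall used above is assumed. If LDL-C is taken as 50-70% of total cholesterol and carries the whole fall, a 10% total fall needs an LDL-C fall of 14-20% (0.10/0.7 to 0.10/0.5). A 20% total fall needs 29-40%, so the upper end is demanding.
- **Over-correction.** If a sterol does not follow total cholesterol at all, its ratio rises by 1/(1 - f) - 1 with no real change: 11.1% at f = 10% and 25.0% at f = 20%. The ratio is therefore not free of artefact.
- **Importance.** The sterols are one of seven groups of exploratory variables in a 46-patient proof-of-concept study, and the plan attaches no hypothesis or decision rule to them.

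A reader might also infer that total cholesterol goes unused. It does not: SAP 3.4 summarises the lipid profile by visit and arm, and patient listings will be produced. What is missing is a prespecified corrected form of the sterol endpoints.

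**Conclusion.** The gap is real but minor. SAP 3.2 provides only uncorrected concentrations, and a treatment difference in either cannot be separated from the intended fall in carrier cholesterol. With an unchanged ratio, a 10-20% cholesterol fall would lower the concentration by 10-20%, and ratio rises of up to 11-25% would be masked. This rests on the assumed falls and on proportional tracking with total cholesterol; the significance and power figures also rest on the assumed SDs and on all 23 patients per arm being measured.

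A reader might go further and infer that the sterol change simply mirrors the LDL-C effect. The identity does not support that. The concentration is the product of the carrier effect and the marker change, and a 20% ratio rise still shows as +8% when cholesterol falls by 10%. The endpoint is confounded, not a copy of LDL-C. Nor can it be said that a mechanistic conclusion would be wrong, since the plan commits to none. The primary analysis, sample size and significance level are untouched.

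**What to change.** In SAP 3.2, under the exploratory endpoints, add lanosterol/total cholesterol and beta-sitosterol/total cholesterol, both values taken from the same visit's fasting lipid panel. Give them the same change-from-baseline summaries and MMRM as the concentrations. The log scale is preferable, because there the concentration effect splits exactly into a ratio part and a cholesterol part.

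Keep the protocol-listed concentrations beside the ratios rather than replacing them. State that any comment on cholesterol synthesis or absorption will rest on both forms together. SAP 1.3 says the sterol results were withheld until after database lock. The ratios should be defined before those results are seen; if they are defined later, they should be labelled post hoc.

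The cost is two derived variables and two more sets of exploratory output, with no new sampling. The downside is possible over-correction if a sterol does not track total cholesterol proportionally; showing both forms lets a reader see it.
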